## 8.6 GENERAL STATISTICAL CONSIDERATIONS

### 8.6.1 Analysis Populations

The **Intent-to-Treat (ITT)** population is defined as the set of subjects who were enrolled or randomized and have at least one dose of PRO 140.

The **Per Protocol (PP)** population is defined as the set of subjects who meet the ITT population requirements, and were not associated with a major protocol violation.

The **Safety** population is defined as all subjects who received at least one dose of PRO 140. This population will be used for the analysis of safety parameters.

### **8.6.2 Statistical Methods**

All collected study data will be presented in subject data listings. Statistical analyses will be performed using SAS® for Windows, version 9.3 or later.

A SAP will be developed and approved before the database is locked. The SAP will present the detailed statistical methodology to be used in analyzing the efficacy and safety data from this trial.

### **8.6.3 Prognostic Factors/Covariates**

There are no pre-planned covariates analyses of the data from this study, other than the baseline of the dependent variable (i.e., Baseline CD4 cell counts for assessing changes in CD4)

### **8.6.4 Handling of Missing Data**

For the per protocol analyses of efficacy outcome measures there will be no imputation of missing data. However, missing data will be imputed using different methods that will be detailed in the SAP for the ITT population of the primary and secondary outcome measures.

### **8.6.5 Multicenter Study**

This is a multicenter clinical trial.

## **8.7 DATA SUMMARY**

### **8.7.1 Subject Disposition**

The disposition of all subjects who sign an ICF will be provided. The number of subjects screened, received treatment, completed, and discontinued during the study, as well as the reasons for all post treatment discontinuations will be summarized. Disposition and reason for study discontinuation will also be provided as a by-subject listing.

### **8.7.2 Demographic and Baseline Characteristics**

Demographics and baseline characteristics (i.e., Age, Gender, Time since HIV diagnosis, Viral load at Screening Visit, etc.) will be summarized using appropriate descriptive statistics.

Medical history of the subjects will also be provided as a by-subject listing.

### **8.7.3 Prior and Concomitant Medications**

Prior and concomitant medications will be summarized for the Safety population. All prior and concomitant medications recorded in the eCRFs will be coded to generic term and all matching Anatomic Therapeutic Classification (ATC) codes using WHO Drug Summaries will be prepared using the coded terms. All prior and concomitant medications recorded in the eCRFs will also be listed.

#### **8.7.4 Efficacy Analysis**

All data from the primary and secondary outcome measures will be summarized and tabulated according to the variable type:

- Time to event data will be depicted using Kaplan-Meier plots
- Continuous data summaries will include number of observations, mean, standard deviation, median, and minimum and maximum values.
- Categorical data summaries will include frequency counts and percentages.

##### **8.7.4.1 Primary Analysis**

Primary Analysis of the primary and secondary outcome measures will be conducted on the ITT population. A statistical analysis plan will be developed to detail the statistical methods used for the primary analysis.

##### **8.7.4.2 Supportive Analysis**

To assess the consistency of the Primary Analysis results, supportive analysis will be conducted using the PP population. Statistical methodology for the supportive analyses will be the same as that of the primary analysis, with the exception of the analysis population used. The PP population will be used for the supportive analysis while the ITT population will be used for the primary analysis.

#### **8.7.5 Safety Analysis**

The Safety population will be used for the analysis of safety assessments.

For continuous variables data will be summarized using n, mean, Standard Deviation (SD), minimum and maximum values. For categorical variables data will be summarized using frequency and percentage.

##### **8.7.5.1 Adverse Events**

Adverse events will be coded using Medical Dictionary for Regulatory Activities (MedDRA). TEAEs are defined as events with an onset on or after the first treatment. TEAEs will be summarized by treatment group, System Organ Class, and preferred term. The following TEAE summaries will be provided:

- TEAEs by severity grade
- TEAEs by relationship to study treatment.

In addition, separate summaries of SAEs, and AEs resulting in discontinuation of study treatment will be presented.

##### **8.7.5.2 Tolerability Assessment**

All data from tolerability assessments of repeated subcutaneous administration of PRO 140 as assessed by study participants (using Visual Analogue Scale) and by Investigator-evaluation of injection site reactions will be summarized.

#### **8.7.5.3 Clinical Laboratory Data**

All laboratory values will be listed. Laboratory measurements will also be summarized.

#### **8.7.5.4 Physical Examination**

All physical examination findings will be listed and any abnormality will be summarized.

#### **8.7.5.5 Vital Signs**

All vital sign assessment findings will be listed and summarized.

#### **8.7.5.6 ECG Examination**

All ECG examination findings will be listed and any abnormality will be summarized.

#### **8.7.5.7 Neurological Assessment**

All neurological assessment findings will be listed and any abnormality will be summarized.

## 9 ADVERSE EVENTS (DEFINITIONS AND REPORTING)

The Investigator is responsible for the detection and documentation of events meeting the criteria and definition of an AE or SAE, as provided in this protocol. During the study when there is a safety evaluation, the Investigator or site staff will be responsible for detecting, documenting, and reporting AEs and SAEs as detailed in this section of the protocol.

### 9.1 ADVERSE EVENT

An adverse event (AE) is defined as any unfavorable or unintended sign, symptom, or disease that occurs or is reported by the subject to have occurred, or a worsening of a pre-existing condition. An AE may or may not be related to the study treatment.

AEs will be elicited through direct questioning and subject reports. Any abnormalities in visit evaluations, physical examination findings or laboratory results that the Investigator believes are clinically significant to the research subject and that occurred after initiation of the first study treatment will be reported as AEs. Abnormal findings that are NOT clinically significant (NCS) should not be recorded as an AE.

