
As shown in Table 0-2, Group A subjects that elect to participate in Part 2 of Treatment Phase after experiencing virologic failure (defined as two consecutive HIV-1 RNA levels of <math>\geq 200</math> copies/mL) during Part 1 of Treatment Phase will receive PRO 140 525mg SC weekly injection for remainder of 48-week Treatment Phase. Should subject experience subsequent virologic failure in Part 2 of Treatment Phase, subject will complete Virologic Failure (VF) Visit assessments and then enter the Follow-up Phase of the study.
 
Table 0-2: Part 2:Rescue Arm for Group A subjects [PRO 140 525mg]
 
 
 PRO 140 525mg	Parenteral solution	175 mg/mL	2 injections of PRO 140 (2 X 1.5 mL/inj.) for remainder of treatment phase	SC injection	
 
 
As shown in Table 0-3, Group B subjects that elect to participate in Part 2 of Treatment Phase after experiencing virologic failure during Part 1 of Treatment Phase will receive PRO 140 700mg SC weekly injection for remainder of 48-week Treatment Phase. Should subject experience subsequent virologic failure in Part 2 of Treatment Phase, subject will complete Virologic Failure (VF) Visit assessments and then enter the Follow-up Phase of the study.
 
Table 0-3: Part 2:Rescue Arm for Group B subjects [PRO 140 700mg]
 
 
 PRO 140 700mg	Parenteral solution	175 mg/mL	2 injections of PRO 140 (2 X 2 mL/inj.) for remainder of treatment phase	SC injection	
 
 
Group A or Group B subjects that do not elect to participate in Part 2 of Treatment Phase and all Group C subjects who experience virologic failure (defined as two consecutive HIV-1 RNA levels of <math>\geq 200</math> copies/mL) at any time during the Treatment Phase will undergo the Virologic Failure (VF) Visit assessments and then exit the Treatment Phase to enter the Follow-up Phase of the study.
 
Subjects who do not experience virologic failure will enter the Follow-up Phase of the study at the end of 48-week Treatment Phase.
 
All study subjects will re-initiate their previous antiretroviral regimen or an alternative regimen selected by their treating physician:
 
 
• One week prior to the end of 48-week Treatment Phase, or
 
• During the Treatment Phase, if virologic failure occurs or have met any other criteria for discontinuation of study treatment as specified in Section 5.2.1 of the protocol.
 
 
Efficacy assessments will include viral load measurement and CD4 cell counts at every alternate week during the first 16 weeks of Treatment Phase and once every four weeks during the remaining 32 weeks of Treatment Phase. Safety assessments will consist of determining and recording all AEs and SAEs; laboratory evaluation of hematology, blood chemistry, and urine analysis; periodic measurement of vital signs; and the performance
					PRO 140 525mg	Parenteral solution	175 mg/mL	2 injections of PRO 140 (2 X 1.5 mL/inj.) for remainder of treatment phase	SC injection	PRO 140 700mg	Parenteral solution	175 mg/mL	2 injections of PRO 140 (2 X 2 mL/inj.) for remainder of treatment phase	SC injection

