#### 7.5 PRIOR / CONCOMITANT MEDICATIONS AND NON-STUDY TREATMENTS

A complete history of antiretroviral therapies will be recorded in the source documents and on the appropriate page of the eCRF.

In addition to this, all other medications and therapies administered or taken by the subject beginning 30 days prior to first Screening Visit and throughout the study will be recorded. Subjects must be questioned at each study visit concerning any new medications or changes in current medications including over-the-counter medication.

For each medication and non-study treatment, the following will be documented:

- Medication/treatment name (generic name may be used if trade name is unknown)
- Dose, unit, and frequency of dosing (individual dosages, not total daily dose).
  - **Note:** *Each new dose of medication should be recorded as a separate entry, with the exception of medications that are given on a sliding scale. For these, it is acceptable to enter the range of the dosage, including the start and stop dates for which the specified dosage range was used.*
- Route of dosing
- Indication for use
- The start date
- The stop date (if medication/therapy is not ongoing)

Please refer to Exclusion Criteria ([Section 3.3.2](#)) for a list of prohibited treatments and/or procedures. All other medications that are appropriate for the care of the subject may be prescribed. If concomitant medications are started during the study, the indication for the concomitant medication should be considered an AE.

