#### 7.10.9 Plasma HIV-1 RNA level and TruCount T Assay

- Frequency of testing: At SV, T1, T2, T4, T6, T8, T10, T12, T14, T16 and T17, at least once every four weeks between T18-21, T22-25, T26-29, T30-33, T34-37, T38-41, T42-45, T48 and at VF visits when subject comes to clinic. In addition, blood sample will also be collected at all Virologic Failure Follow-up (VF-FU) Visits or Non-Virologic Failure Follow-up (NVF-FU) Visits.
- To assess antiretroviral therapeutic response to PRO 140 or cART regimen

**Note:** Plasma HIV-1 RNA level will be measured using Human Immunodeficiency Virus 1 (HIV-1), Quantitative, RNA (Taqman® Real-Time PCR) test.

TruCount T Assay includes measurement of Absolute Lymphocytes, CD3 cell count, CD4 cell count, CD8 cell count, CD3%, CD4% and CD8%

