#### **7.10.16 Genital Secretion sample collection for GU sub-study**

- Frequency of testing: At the T1 (prior to first dose of PRO 140), T4, T16 and VF visits.
- In a subset of participants (n=20) to assess the extent of PRO 140 entry into the genitourinary compartment, and to evaluate virologic responses in genital secretion.

All laboratory reports will be reviewed by the Investigator.

Post-treatment abnormal results that are considered by the Investigator to be clinically significant will be recorded as adverse events. If the Investigator judges it necessary, testing may be repeated in order to make the determination of clinical significance. Validated, quality-controlled laboratory data will be transferred to the main database for analyses.

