8.2.1.1 Adverse Events

Adverse events will be coded using Medical Dictionary for Regulatory Activities (MedDRA). TEAEs are defined as events with an onset on or after the first treatment. TEAEs will be summarized by treatment group, System Organ Class (SOC), and preferred term (PT). The following TEAE summaries will be provided:

- Overall (*i.e.*, regardless of severity or relationship to treatment)
- By severity grade (mild, moderate, severe, life threatening or death for SAEs)
- By relationship to study treatment (definitely related, probably related, possibly related, remotely related or unrelated)

In addition, separate summaries of SAEs, and AEs resulting in discontinuation of study treatment will be presented.

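### The AE rules leave open whether virologic failure is recorded as an adverse event, and the SAP safety tables by dose have no filter for it

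*Protocol*

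**What the plan says.** Three protocol sentences bear on whether a viral rebound is an AE.

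- Protocol 9.1 covers "Any abnormalities in visit evaluations, physical examination findings or laboratory results that the Investigator believes are clinically significant" and that arise after the first study treatment. Its converse is "Abnormal findings that are NOT clinically significant (NCS) should not be recorded as an AE". The definition in the same section also takes in deterioration of a condition already present.
- The closing text of Protocol 7.10 (printed after 7.10.16) says: "Post-treatment abnormal results that are considered by the Investigator to be clinically significant will be recorded as adverse events". It names no exception. Section 7.10.9, "Plasma HIV-1 RNA level and TruCount T Assay", lies within 7.10.
- Protocol 7.5 says: "If concomitant medications are started during the study, the indication for the concomitant medication should be considered an AE". It does not exempt antiretroviral therapy (ART), and 7.5.1 speaks of antiretrovirals as concomitant therapy.

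Other passages keep viral load and failure apart from AEs.

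- The Protocol Synopsis says "Efficacy assessments will include viral load measurement and CD4 cell counts at every alternate week", and names hematology, chemistry and urine testing as the safety laboratory work.
- Protocol 5.2.1 lists virologic failure as its own ground for stopping treatment.
- Protocol 12 lists virologic rebounds beside AEs among the signals that the monitoring committee reviews.
- SAP 8.2.1.4 does not name HIV-1 RNA among the safety laboratory evaluations.

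On analysis, SAP 8.2.1.1 tabulates TEAEs by treatment group, system organ class and preferred term, and adds that "separate summaries of SAEs, and AEs resulting in discontinuation of study treatment will be presented". It has no rule for terms that represent virologic failure.

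**The concern.** TEAE incidence is a primary safety outcome, reported within each dose group (Protocol 8.2.1; SAP 3.1 and 3.1.1). Virologic failure is an efficacy outcome, and Protocol 1.5 gives reasons to expect less of it at the higher doses. If some failures are entered as AEs, the overall safety percentages by dose partly measure efficacy.

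The literal rules make this easy. A confirmed rise to 200 copies/mL or more ends the assigned dose and leads either to ART or to a higher dose, so an investigator would find it hard to call the result not clinically significant. The AE form also records whether study treatment was discontinued because of the event (Protocol 9.1.2), so a failure entered as an AE has a direct path into the discontinuation summary. The study is open label, with up to 60 centers and no written rule, so different practice between sites is foreseeable. No inferential analysis is planned (SAP 7.3 and 7.4), so readers will rely on the raw tables.

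**Working it through.** **Step 1: the text.** Neither document states that virologic failure is to be recorded as an AE, and neither states that it is not. Protocol 9.1, 7.5 and the end of 7.10 permit it. The Synopsis, Protocol 5.2.1 and 12, and SAP 8.2.1.4 suggest separate handling but give sites no instruction. The plan has no figure to reproduce here: the sample size rests on clinical judgment and no effect size is stated.

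**Step 2: size in the TEAE table (illustration).** Inputs:

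- t, the share of subjects with a TEAE from other causes: 29/43 = 0.674, from the earlier 12-week study at 350 mg (Protocol 1.4.2.7). So 1 - t = 14/43 = 0.326.
- p, the failure rate by group: assumed 60% (Group A) vs 30% (Group C), and 40% vs 30%. The documents give no failure rate for these doses over 48 weeks under this definition.
- q, the share of failures recorded as AEs: unknown, 0 to 1, taken as equal in both groups.
- Failure is taken as independent of other TEAEs.

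TEAE incidence = t + (1 - t) × q × p. The A-minus-C difference due to failure alone = (1 - t) × q × (pA - pC).

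| q | 60% vs 30% | 40% vs 30% |
|---|---|---|
| 0 | 0 | 0 |
| 0.25 | 0.326 × 0.25 × 0.30 = 2.4 points | 0.326 × 0.25 × 0.10 = 0.8 points |
| 0.5 | 4.9 points | 1.6 points |
| 1 | 9.8 points | 3.3 points |

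The difference is proportional to 1 - t. If more than 67% of subjects have another TEAE over 48 weeks, it shrinks. If the 29/43 already contains failures recorded as AEs, it grows. The documents settle neither.

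**Step 3: size in the AE-discontinuation table (illustration).** Let r be the share of failures who stay on PRO 140 through rescue. Group C has no higher dose to move to, so r = 0 there. The incidence due to recorded failures = q × p × (1 - r). With q = 1:

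| r in Group A | 60% vs 30% | 40% vs 30% |
|---|---|---|
| 0 | 0.60 - 0.30 = +30 points | +10 points |
| 0.5 | 0.30 - 0.30 = 0 | 0.20 - 0.30 = -10 points |
| 1 | 0 - 0.30 = -30 points | -30 points |

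The sign changes at r = 1 - pC/pA, which is 0.50 in the first case and 0.25 in the second. A rescued subject who fails again and then leaves treatment would count as not retained, which lowers the effective r. At q = 0.25 the 60% vs 30% range is +7.5 to -7.5 points.

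**Step 4: the ART-restart route.** Protocol 4.2.3 has subjects who remain suppressed restart ART at Week 47. Read literally, 7.5 would therefore give them an AE as well. This route inflates the count and adds site variation, but it does not single out the dose with more failures.

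**The case against.** The strongest reply is that the plan's structure shows an intention to keep failure out of the AE data. Viral load is classed as efficacy, failure has its own discontinuation ground, the committee list separates rebounds from AEs, and SAP 8.1.5 reports ART and its re-initiation apart from concomitant medications (SAP 8.1.4). Experienced sites may follow that intention, in which case q is near 0 and nothing is distorted. The summary of the earlier study gives infections and infestations as the most common AE category (14 of 43), which may mean that failures were not routinely recorded there. That is suggestive at most, because the exact failure count, the coding and that study's AE rule are not given.

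The harm is also bounded. TEAEs are shown by preferred term, grade and relationship, with by-subject listings, so a viral-load term would have its own row and the toxicity rows would be unchanged. Failure by group is reported separately (SAP 8.2.2.1), and nothing is tested.

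These points stand as limits on size. They do not close the gap. None of the cited passages instructs a site, and row-level detail does not correct the overall TEAE percentage or the AE-discontinuation total.

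Two stronger readings are tempting. A reader might infer that failures must be, and will be, in these tables. The documents do not support that, because Protocol 9.1 and 7.10 make entry depend on what the investigator considers clinically significant. A reader might also infer that the more effective dose will look safer throughout. That holds for overall TEAE incidence only to the extent that failures are recorded, and Step 3 shows that it can reverse for discontinuations.

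**Conclusion.** The point holds as an unresolved recording rule with no analysis safeguard, and it should be corrected. The AE rules permit HIV-1 RNA rebound, virologic failure or ART restart to be recorded as AEs at the investigator's judgment, other passages treat viral load and failure separately, and the SAP tables take whatever was recorded. Efficacy differences between doses can therefore enter overall TEAE incidence and AE discontinuations, to an extent that may differ by site.

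On the assumptions above, the effect on the A-minus-C TEAE difference is 0 to about 10 points with failure rates of 60% vs 30%, and 0 to about 3 points with 40% vs 30%. In the discontinuation table its direction cannot be predicted. The failure rates, q and r are assumptions. The earlier study cannot supply them: 23 of its 43 subjects completed without failure, but over 12 weeks, at 350 mg only and with a 400-copy threshold. A single headline inflation figure built on that study would be a worst case and not an estimate.

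**What to change.** **SAP 8.2.1.1 (the main change).** Produce the overall TEAE and AE-discontinuation tables by dose twice: with all terms, and without preferred terms for viral load increase, virologic failure, and HIV infection recorded only as the indication for restarting ART. Make the version without them the main display. Fix the term list before database lock, and list the excluded records separately by subject, with dose and site.

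**Protocol.** Reconcile 9.1, 7.5 and the closing text of 7.10 with the Synopsis, so that virologic failure is captured as an efficacy endpoint and recorded as an AE only when it is part of a clinical event or a serious AE.

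The protocol change is not enough alone. The first approximately 150 subjects all received 350 mg and the 700 mg group enrolls last, so a recording rule introduced mid-trial would make AE capture differ by dose. The SAP exclusion applies to all cohorts alike and also repairs data already entered.

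Cost: one term list, slightly more tabulation, and a lower headline AE count. No new data are needed.

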#### 9.1.1 Reporting of Adverse Events

Report initiation for all AEs and SAEs will begin at the time of the first treatment visit and continue up until the final study visit (i.e. up to NVF-FU2 for subject who do not experience virologic failure or until viral suppression is achieved for subjects who experience virologic failure). Additionally, virologic failure subjects will have a long-term follow-up visits at 6 months and at one year from the time of the Virologic Failure Visit. Only SAEs and any AE that is considered possibly or probably or definitely related to the study treatment by the Investigator will be captured during the Long-term Follow-up Phase of the study. All events will be followed to resolution or until 30 days after the subject completes the study. A final assessment of outcome will be made at that time.

All AEs must be recorded in the subject's medical records and on the eCRFs. AEs will be reported using customary medical terminology along with the following information: the onset and end dates, whether the event is considered to be a SAE (see [Section 9.2](#)), the impact the event had on study treatment (see [Section 9.1.2](#)), the DAIDS AE grade (intensity) of the event (see [Section 9.1.3](#)), the causality of the event (see [Section 9.1.4](#)), whether treatment was given as a result of the event (see [Section 9.1.5](#)), and the outcome of the event (see [Section 9.1.6](#)).

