**Table 4-3: Schedule of Assessments –Follow-Up (FU) Phase**

## (a) Subjects who do NOT experience Virologic Failure

Procedure/Assessments	Follow-Up Visit -1	Follow-Up Visit -2
	NVF-FU1	NVF-FU2
Window Period	2 weeks (±3 days) after T48	4 weeks (±3 days) after T48
Physical Examination	X 	X 
Vital Signs	X	X
Plasma HIV-1 RNA level	X	X
TruCount T assay	X	X
Anti-idiotypic Antibodies to PRO 140		X
Re-initiate combination Antiretroviral Therapy	X	X
Adverse Events	X	X
Concomitant Medications	X	X

[1] Symptom-directed physical examination

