## (b) Subjects who experience Virologic Failure

## • Short-Term Follow-Up Visits

Procedure/Assessments	Follow-Up Visit -1	Follow-Up Visit -2	Follow-Up Visit -3 
	VF-FU1	VF-FU2	VF-FU3
Window Period	4 weeks (±7 days) after VF visit	8 weeks (±7 days) after VF visit	12 weeks (±7 days) after VF visit
Physical Examination	X 	X 	X 
Vital Signs	X	X	X
Plasma HIV-1 RNA level	X	X	X
TruCount T assay	X	X	X
Anti-idiotypic Antibodies to PRO 140	X		
Re-initiate combination Antiretroviral Therapy	X	X	X
Adverse Events	X	X	X
Concomitant Medications	X	X	X

[1] Subject will be followed up every 4 weeks until viral suppression is achieved (i.e., plasma HIV-1 RNA levels decline to < 50 copies/mL). Subject will undergo additional follow-up visits every 4 weeks beyond VF-FU3 visit (up to a maximum of 6 months after re-initiation of combination antiviral therapy), if viral suppression is not achieved at the end of VF-FU3 visit.

[2] Symptom-directed physical examination

- Long-Term Follow-Up Visits

Procedure/Assessments	Long-Term Follow-Up Visit -1	Long-Term Follow-Up Visit -2
	VF-6mFU	VF-12mFU
Window Period	6 months ( $\pm 1$ month) after VF visit	12 months ( $\pm 1$ month) after VF visit
Adverse Events 	X	X
Assessment of cART changes 	X	X
Plasma HIV-1 RNA level	X	X
TruCount T assay	X	X
Trofile ® DNA or RNA Assay 	X	X
PhenoSense ® Entry Assay 	X	X
HIV-1 Drug Resistance Assay 	X	X

[1] Only SAEs and any AE that is considered possibly or probably or definitely related to the IP by the investigator will be captured during the long term follow up phase.

[2] Any changes to the combination antiretroviral regimen since the viral re-suppression is achieved.

[3] Monogram Biosciences Trofile® DNA or RNA (or both) assay will be performed depending on last known HIV-1 RNA levels.

[4] Monogram Biosciences HIV-1 PhenoSense® Entry assay with AMD3100 (X4 inhibitor drug), Maraviroc and PRO 140 (R5 inhibitor drugs).

[5] Monogram Biosciences GenoSure Archive Assay or PhenoSense® GT (and PhenoSense Integrase and GeneSeq Integrase testing, if applicable), will be performed depending on last known HIV-RNA levels.

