8.1 Summarizing and Tabulating the Collected Data

All data collected will be summarized according to the variable type:

- Continuous data summaries will include number of observations, mean, standard deviation, median, and minimum and maximum values.
- Categorical data summaries will include frequency counts and percentages.

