8.1.6 Treatment Exposure

All data from administration of study drug will be presented. In addition the following summaries will be included:

- Duration of PRO 140 treatment (in weeks)
 - At the Assigned dose
 - At the Rescue Dose (if applicable)
 - Combined Assigned and Rescue dose.
- Proportion of participants completing 24, 48 weeks of PRO 140 treatment.
 - At the Assigned dose
 - Combined Assigned and Rescue dose
- Duration of PRO 140 treatment (in weeks) at the time of virologic failure

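### Time at risk for adverse events depends on virologic outcome, event type and access to rescue, yet TEAEs are to be reported by dose as crude percentages with no end date

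*Protocol*

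**What the plan says.** **Collection.** Protocol 9.1.1 runs reporting of all AEs from the first treatment visit "up to NVF-FU2 for subject who do not experience virologic failure or until viral suppression is achieved for subjects who experience virologic failure". NVF-FU2, the last visit for non-failures, falls "4 weeks (±3 days) after T48" (Protocol Table 4-3(a)). Failures are seen 4, 8 and 12 weeks after the VF visit and then every 4 weeks until RNA is below 50 copies/mL, "up to a maximum of 6 months after re-initiation of combination antiviral therapy" (Table 4-3(b)). In the long-term follow-up at 6 and 12 months after the VF visit, "Only SAEs and any AE that is considered possibly or probably or definitely related to the study treatment by the Investigator will be captured" (Protocol 9.1.1; also 4.4.1.2).

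**Rescue.** Under Protocol Sections 3 and 4.2, failures in Groups A and B may stay on PRO 140 at a higher dose in Part 2 for the rest of the 48 weeks. Failures in Group C leave the Treatment Phase.

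**Analysis.** SAP 8.2.1.1: "TEAEs are defined as events with an onset on or after the first treatment". No closing date is given. TEAEs are tabulated by treatment group, and SAP 8.1 sets the format: "Categorical data summaries will include frequency counts and percentages". SAP 8.1.6 summarizes weeks of treatment at the assigned, rescue and combined dose, but nothing links those weeks to AE incidence. Incidence of TEAEs, of treatment-emergent SAEs and of Grade 3 or 4 events are primary safety outcomes, to be shown within each dose group (SAP 3.1 and 3.1.1).

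**The concern.** A crude percentage compares groups fairly only if their members were watched for similar lengths of time. Here the watching time follows from the efficacy result. A completer is observed for all AEs to about week 52. A subject who fails early and leaves treatment may be observed for a third of that. For SAEs and related events the same subject is observed for longer than a completer. Whether a failure leaves at all depends on the dose group.

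Two doses with identical toxicity can therefore show different percentages, and the difference can point one way for ordinary AEs and the other way for SAEs. The planned tables would not let a reader undo this. Deciding whether Part 2 events count under the assigned or the rescue dose, which the SAP also leaves open, would not equalize the time at risk.

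**Working it through.** **1. The plan's own figure.** Screening 6 + treatment 48 + follow-up 4 = 58 weeks, which matches the total study duration in SAP 2.3. The all-AE window from first dose for a non-failure is 48 + 4 = 52 nominal weeks.

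**2. Windows for a failure who leaves treatment.** All-AE window = failure week + 4, 8 or 12, according to the visit at which RNA is below 50. SAE and related-AE window = failure week + 52.

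| Failure week | All AEs (weeks) | SAEs and related AEs (weeks) | Non-failure (weeks) |
|---|---|---|---|
| 8 | 12 to 20 | 60 | 52 |
| 12 | 16 to 24 | 64 | 52 |
| 24 | 28 to 36 | 76 | 52 |
| 44 | 48 to 56 | 96 | 52 |

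Early failures lose most of the all-AE window; late failures lose little or none.

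**3. Effect on crude percentages.** The documents give no failure timing, failure rate, rescue uptake or AE rate by dose for this trial. Everything in this step is assumed: the same constant AE hazard in both arms, exponential failure times with 50% or 20% failing by week 48, all-AE collection ending 8 weeks after failure, and no rescue.

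- AE hazard: λ = −ln(1 − p)/52, where p is the true 52-week risk. For p = 0.30, λ = 0.00686 per week.
- Failure hazard: θ = −ln(1 − f)/48. For f = 0.50, θ = 0.01444; for f = 0.20, θ = 0.00465.
- Window: W = min(T + 8, 52) for failure at week T < 48, otherwise W = 52.
- Crude incidence = 1 − E[exp(−λW)], by numerical integration over T.

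| True 52-week risk | Lag (weeks) | 50% failing | 20% failing |
|---|---|---|---|
| 30% | 8 | 23.9% | 27.8% |
| 30% | 4 | 22.8% | 27.3% |
| 30% | 12 | 24.9% | 28.2% |
| 60% | 8 | 49.2% | 56.1% |

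Mean all-AE window at the 8-week lag: 40.6 versus 47.8 weeks.

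A case that can be checked by hand: all failures at week 12, re-suppression 8 weeks later, 60% versus 20% failing, true risk 50%. Then λ = ln 2/52 = 0.01333, and the risk over 20 weeks is 1 − exp(−0.2666) = 0.234. Crude incidence is 0.6 × 0.234 + 0.4 × 0.5 = 34.0%, against 0.2 × 0.234 + 0.8 × 0.5 = 44.7%.

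**4. SAEs and related AEs.** Same failure assumptions, with W = T + 52 for failures (full long-term follow-up assumed) and p = 0.10. Mean windows are 62.6 versus 56.6 weeks, and crude incidence is 11.9% versus 10.8%. The failing arm now looks worse.

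**5. Rescue.** Let a share r of failures in the 50%-failing arm (A or B) enter Part 2 and be observed to week 52, against a 20%-failing Group C with no rescue. Crude incidence in the failing arm is then 23.88 + r × (30.00 − 23.88) percent. Setting this equal to 27.76 gives r = 3.88/6.12, about 63%. Above that the all-AE gap reverses; at r = 100% it is 30.0% versus 27.8%.

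**6. Person-time.** Under a constant hazard, subjects with a first event divided by person-weeks to first event or end of window estimates λ in both arms: 0.69 per 100 person-weeks at p = 0.30. If the hazard is instead three times higher in the first 12 weeks (assumed, same 30% risk), the rates are 0.78 versus 0.74. Person-time removes most of the distortion, not all of it.

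**The case against.** The SAP plans no inferential statistics (7.3 and 7.4), so no test or decision rule rests on these percentages, and SAP 8.1.6 already shows unequal treatment durations. SAEs and related AEs, the events that matter most, are followed longer in failures, not for less time. Group A and B failures can remain under full observation in Part 2.

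Much of this stands, and it limits the point. A reader might infer that the dose with more early failures will simply look safer. The documents do not support that. It holds only for non-serious events judged unrelated or remotely related, in failures who do not take rescue. It is wrong for SAEs and related events, and it can be wrong for all AEs when rescue uptake is high. Protocol 1.5 expects fewer low troughs at 525 mg and 700 mg, so the dose most likely to fail, 350 mg, is one that has a rescue option.

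The descriptive design is not a full answer. With no model or test, the side-by-side percentages are the safety result. Treatment duration in a separate table shows that exposure differs, but it is not time at risk: it omits follow-up after the last dose and is not stopped at the first event.

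**Conclusion.** The point holds in a limited form. As written, the plan produces incidences by dose that are not comparable, because time at risk varies with virologic outcome, event type and the availability of rescue. On the stated assumptions the distortion is about 4 points for a true 30% non-serious, not-related event (in favor of the failing dose) and about 1 point for a true 10% SAE or related event (against it). The first reverses when rescue uptake in the failing arm exceeds about 63%. These figures illustrate and do not predict: without failure and rescue rates by dose, the actual size and the favored dose cannot be determined. This should be corrected in the SAP. It affects how the primary safety tables read, not a test.

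**What to change.** **SAP 8.2.1.1, window.** Define one TEAE window for all subjects, from first dose to a fixed cut-off after the subject's actual last PRO 140 dose (for example 28 days), ended earlier if all-AE collection ended earlier. Anchor it to the last dose and not to VF-FU1: that visit is timed from the VF visit with a ±7-day allowance, and Protocol 4.2 lets dosing continue after failure while a new regimen is arranged. List later SAEs and related AEs separately.

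**SAP 8.2.1.1, rate.** Beside each crude percentage, report subjects with a first event per 100 person-weeks at risk. Count person-time from first dose to the earliest of first event, end of the window, or end of all-AE collection. Derive it from dosing, AE-onset and visit dates, not from the durations in 8.1.6. Because the rate assumes a roughly constant hazard, add a Kaplan-Meier or cumulative-incidence estimate of time to first event for any TEAE and for Grade 3 or 4 events.

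**Protocol.** Reconcile 9.1.1, which read literally ends all-AE collection at re-suppression, with Table 4-2, which records AEs at every treatment visit. The conflict affects Part 2 subjects who re-suppress while still being dosed.

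**Cost.** SAP wording, one extra table column, a few time-to-event summaries and the Protocol clarification. No new data are needed.
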